5.2. Key Definitions

5.2.1. Date of First Dose of Study Treatment

The date of first dose of study treatment will be the date of the Baseline visit, at which the randomized study treatment is dispensed. Patients are to be instructed to apply the first dose at home that evening. Patients who do not have confirmation of study treatment administration (defined as non-zero number of doses taken, on a study drug compliance eCRF at the Month 1.5 visit) will not have a date of first dose defined. If a patient takes zero doses before the Month 1.5 visit but does take subsequent doses, the date of first dose will reflect the date of dispensation of the first study treatment applied.

5.2.2. Baseline Values

The baseline assessment will be the last available measurement taken on or before the date of first dose of study treatment, including any assessments at unscheduled visits. Measurements taken on the date of first dose of study treatment will be considered to be taken prior to first dose. Baseline values are typically collected at the Baseline visit.

5.2.3. Study Day

Study day is calculated as (date - first dose date of study medication +1) for dates on or after first dose, and (date - first dose date) for dates before the first dose date. Therefore, the first dose date is Study Day 1, and the day immediately prior is Study Day -1. The first dose date of study medication will be based on the application of Vaseline while onsite during the Baseline visit. The first application of randomized study medication is expected to be applied that evening.

5.2.4. Change from Baseline to Post Study Medication Visits

Change from Baseline is (value - baseline value) and is calculated for subjects with both non-missing baseline values and non-missing post-baseline values.

5.2.5. Tear Break-up Time

The TBUT for a patient is calculated as average of 3 separate measurements for each eye separately.

5.2.6. Ocular Surface Disease Index Total Score and Subscale Scores

The OSDI questionnaire, provided in [Appendix 2](#), consists of 12 questions regarding ocular symptoms, environmental triggers, and vision-related functioning in patients with DED. The patient will be asked to rate each symptom using a 5-point scale (0 to 4), where 0 = none of the time; 1 = some of the time; 2 = half of the time; 3 = most of the time; and 4 = all the time. There are 7 questions related to visual functioning that allow a response of “N/A” (not applicable).

The OSDI total score (on a scale of 0 to 100) is calculated from the raw scores of each of the 12 questions based on the formula: $([\text{sum of scores for all questions answered}] \times 100) / ([\text{total number of questions answered}] \times 4)$, where questions answered with N/A are considered unanswered and excluded from the calculation. Higher scores represent greater disability.

Subscale scores are calculated similarly, where the Ocular Symptoms subscale includes the 5 questions on light sensitivity, gritty feeling, painful/sore eyes, blurred vision, and poor vision; the Vision Related Function subscale includes the 4 questions on problems reading, driving at night, working with a computer, or watching TV; and the Environmental Triggers subscale includes questions about windy conditions, low humidity, and air conditioning.

5.2.7. Visual Analogue Scale

Individual visual analogue scales will be completed for 7 different symptoms, as provided in [Appendix 1](#). Lower values indicate better results:

- burning/stinging
- itching

- foreign body sensation
- eye discomfort
- eye dryness
- photophobia
- pain

The mean of the completed VAS scores will be calculated to produce the Average VAS score.

The Worst VAS will be defined as the individual VAS with the highest (worst) score at baseline. If two or more VAS results are tied for the highest score at baseline, the average of those two (or more) will be used as the Worst VAS. Changes from baseline at subsequent visits will then be calculated based on the average of those scores at subsequent visits.

5.2.8. Standard Patient Evaluation of Eye Dryness

The SPEED score will be calculated based on occurrence, frequency, and severity of the 4 symptoms of dryness, grittiness or scratchiness, soreness or irritation, burning or watering, and eye fatigue as shown in [Appendix 3](#). Frequency is evaluated on a 4-point scale (0=never to 3=constant) and severity on a 5-point scale (0=no problem to 4=intolerable) for each symptom. The total SPEED score is derived as the sum of the frequency and severity scores across all 4 symptoms, with a range of possible values of 0 to 28, where higher scores indicate increasing severity.

5.2.9. Best Corrected Visual Acuity Logarithm of the Minimal Angle of Resolution

Logarithm of the Minimal Angle of Resolution (LogMAR) will be calculated from the total letter score as $\text{LogMAR} = 1.7 - 0.02 \times (\text{total letter score})$, for each eye.

5.3. Missing Data

Missing efficacy data will be handled as follows:

- The primary efficacy analyses and most other efficacy analyses will utilize multiple imputation.
- Sensitivity analyses will be performed on the primary using the LOCF approach, where non-missing post-baseline values are carried forward to subsequent visits.

Prior to performing imputation or analyses, results from unscheduled visits and early termination (ET) visits (defined as per [Section 5.1](#)) will be mapped to the closest scheduled visit (Day 14, Month 1.5, Month 3, Month 4.5, or Month 6). In other words, a patient with an ET visit at Day 40 would have its those results mapped to the Month 1.5 visit.

Actual item results will be imputed, and any subscale scores, total scores, changes from baseline, responder status, etc. will be derived from the imputed values where necessary.

For safety analyses, where incomplete dates are present, medications will be categorized as concomitant, and adverse events as treatment-emergent, unless sufficient information is present to definitely determine that the medication usage completed, or event resolved, prior to the first dose of study medication.

5.3.1. Multiple Imputation

Missing data will be imputed via multiple imputation (MI) using a Markov Chain Monte Carlo (MCMC) approach. This approach is suitable for non-monotone missingness (missed visits followed by completed visits), incorporates all available observed data as the basis for imputing values, and utilizes the same method to handle all missing data (i.e., not differentiating by cause of missingness). Studies have shown that MI is statistically superior to more traditional methods of imputation (e.g., LOCF; e.g., [DeSouza et al., 2009](#); [Tang et al., 2005](#)).

5.3.1.1. Multiple Imputation for Primary Analysis

Multiple imputation will be performed separately for each assessment; in other words, MGYLS values will not be used to impute OSDI values. The same seed number (utilized in SAS[®] PROC MI) of 135790 will be used throughout. For each MI, 20 imputations will be created, analyses performed on each imputed dataset separately, and results combined using PROC MIANALYZE. The appropriate minimum and maximum values will be used for each variable, and results rounded to the same precision as collected values. Multiple imputation will be limited to patients in the analysis population being used, and will include values that are eligible for use in summaries and analyses as described in [Section 5.1](#) (e.g., unscheduled and early termination visits will be mapped to scheduled visits, and visits with >1 non-missing values mapped to that visit will utilize the later result), through the Month 3 visit. Screening visit values will not be incorporated into the multiple imputation.

The following variables will be included in the multiple imputation model, as numeric variables:

- Treatment group (split into three dichotomous variables)
- Randomization criteria (disease duration category and baseline MGS score category)
- Age
- Sex
- Analysis value (MGYLS or OSDI total score) for each scheduled visit

The following pseudocode will be used:

```
proc mi data=xxx seed=135790 nimpute=20 out=yyy  
    minimum = 0 0 0 18 0 0 0 0 0 0 0
```

```

        maximum = 1 1 1 99 1 1 1  xx xx xx xx
        round =   1 1 1 1  1 1 1  1  1  1  1  ;
var Dur5yr MGSless6 male age trt0_5 trt1_0 trtpbo
    Day1 Day14 Day45 Day90;
mcmc chain=multiple displayinit;
run;

```

<proc genmod, etc.>

```

Proc mianalyze data=xxx (drop=effect);
  by trt01pn;
  modeleffects LSM;
  stderr;
run;

```

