9.1.2 EXPANSION COHORT

Estimates for sample size calculations are from the final Cohort 1 interim analysis from Azura Clinical Protocol AZ201801. The mean response of 0.77 and a standard deviation for MGYLS of 2.28 units was observed for control and a mean response of 2.77 units and a standard deviation for MGYLS of 3.35 units was observed for AZR-MD-001 0.5%. A sample size of 45 subjects per group will have 90% power to detect a difference of 2.0 units between the active treatment group and the placebo group using a two-sample t-test at a significance level of 0.05. The standard deviation for Total OSDI was 6.31 units for control and 8.34 units for the high dose. A sample size of 58 subjects per group will have 90% power to detect a difference of 4.52 units between the active treatment group and the control group using a two-sample t-test at a significance level of 0.05. To allow for additional site to site variability the sample size per group will be increased to approximately 75 patients.

Multiplicity Consideration: To address the multiple primary endpoints defined in this study, the primary endpoints have been prioritized into a hierarchical structure. For example, in order to test the primary symptom endpoint of Total OSDI, the primary sign endpoint of MGYLS must be statistically significantly higher in the AZR-MD-001 treatment group compared to the vehicle treatment group using a two-sided significance level of 0.05 for a given concentration. The final order of the endpoints will be defined in the Statistical Analysis Plan (SAP) prior to unmasking the study. Using this strategy, the family-wise Type I error rate will be maintained at the 0.05 significance level for the two primary endpoints.

Interim Analysis (Primary efficacy endpoint for the US): An interim analysis is planned after the final enrolled patient completes the month 3 visit. Only an independent biostatistician will be unblinded to the treatment patients actually received and only summary efficacy and safety tables will be provided. Outcomes from this analysis will assist in the confirmation of the study power calculations and potentially as part of a rolling submission to global regulatory agencies.

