3. ENDPOINTS

3.1. Efficacy Endpoints

3.1.1. Primary Efficacy Endpoints

Primary efficacy measures are divided into endpoints for primary efficacy signs and primary efficacy symptoms for MGD.

- The primary efficacy sign for MGD is the Change from Baseline at Month 3 in MGYLS (0 to 15 scale; higher scores are better).
- The primary efficacy symptom for MGD is the Change from Baseline at Month 3 in OSDI total score (0 to 100 scale; lower scores are better).

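### Bounding imputed MGYLS values at 0 pulls the first-tested primary difference slightly toward zero; the bounds and rounding can be dropped for the continuous analyses

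*SAP*

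**What the plan says.** SAP 5.3 states that "The primary efficacy analyses and most other efficacy analyses will utilize multiple imputation", and SAP 8.1 makes the ITT Set primary. SAP 5.3.1.1 specifies an MCMC normal-model imputation, run separately for MGYLS and OSDI, and says "The appropriate minimum and maximum values will be used for each variable, and results rounded to the same precision as collected values". The PROC MI pseudocode carries "minimum = 0 0 0 18 0 0 0 0 0 0 0", so the lower limit is 0 for Day 1, Day 14, Day 45 and Day 90, and it rounds those values to 1. The upper limit appears only as the placeholder 'xx'. The 0 to 15 range for MGYLS comes from SAP 3.1.1. Treatment is entered as three 0/1 indicators.

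SAP 8.1.1 tests MGYLS for 0.5% against placebo first, and every later primary test depends on it. The only other imputation planned for the primary endpoints is LOCF (SAP 8.1.2.1).

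On what is imputed, SAP 5.3 says "Actual item results will be imputed, and any subscale scores, total scores, changes from baseline, responder status, etc. will be derived from the imputed values", qualified by 'where necessary'. SAP 5.3.1.1 names the OSDI total score as the analysis value.

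**The concern.** A normal draw confined to values at or above 0 has a mean above the model mean, and the excess grows as the model mean approaches 0. The indicators shift only the mean, so the residual variance is the same in every arm. Placebo has the lowest expected mean, so its imputed values are lifted most and the active-minus-placebo difference among imputed patients shrinks. This happens at the first step of the hierarchy, and no planned analysis isolates it: LOCF differs from the primary method in every respect, not just in the bounds. A comparison of means does not need imputed values to lie on the scale, so the loss buys nothing.

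**Working it through.** **Inputs from the documents.** Mean (SD) MGYLS change: placebo 0.77 (2.28), 0.5% 2.77 (3.35), 1.0% 3.79 (4.11) (SAP Table 1). For control, protocol 9.1.2 agrees: "The mean response of 0.77 and a standard deviation for MGYLS of 2.28 units was observed for control". Pooled SD 3.63 and power 0.918 for 0.5% against placebo (SAP 2.3.2); 75 per arm (SAP 2.3.1); two-sided 0.05.

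**Assumed, because the documents are silent.**
- Baseline mean MGYLS of 1, 2 or 4.
- Residual SD of 2.28 to 3.0. The root mean of the three arm variances, √[(2.28² + 3.35² + 4.11²)/3] = 3.33, serves as an upper limit.
- Missing share at Month 3 of 10% or 20%, equal in all arms.
- Out-of-range draws are redrawn and then rounded. The SAP does not say how they are handled.

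**Step 1, the plan's own figure.** SE = 3.63 × √(2/75) = 0.593 and 2.0/0.593 = 3.37. A two-sided t-test with 148 df has power 0.918, as stated.

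**Step 2, shift of one imputed value.** For model mean μ = baseline + change and SD σ, let α = (0 − μ)/σ and β = (15 − μ)/σ. The shift is σ[φ(α) − φ(β)]/[Φ(β) − Φ(α)]. With baseline 1 and σ = 3.0, placebo has μ = 1.77 and α = −0.59, so the shift is 3 × 0.335/0.722 = 1.39. For 0.5%, μ = 3.77 and the shift is 0.61. Rounding afterwards changes these only to 1.386 and 0.603, so the bound drives the effect. Rounding before the range check makes it somewhat smaller (shrinkage 0.70 instead of 0.78).

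**Step 3, trial-level effect.** Difference = 2.0 − missing share × (placebo shift − 0.5% shift). For baseline 1, σ = 3.0 and 10% missing: 2.0 − 0.10 × 0.783 = 1.92. Power is recomputed with n = 75 and SD 3.63 held fixed.

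| Baseline | Residual SD | Shift placebo / 0.5% / 1.0% | Shrinkage, 0.5% | 10% missing: difference (power) | 20% missing: difference (power) |
|---|---|---|---|---|---|
| 1 | 2.28 | 0.85 / 0.24 / 0.10 | 0.61 | 1.94 (0.901) | 1.88 (0.882) |
| 1 | 3.0 | 1.39 / 0.60 / 0.35 | 0.78 | 1.92 (0.896) | 1.84 (0.871) |
| 2 | 2.28 | 0.49 / 0.10 / 0.04 | 0.38 | 1.96 (0.908) | 1.92 (0.897) |
| 2 | 3.0 | 0.95 / 0.35 / 0.18 | 0.59 | 1.94 (0.902) | 1.88 (0.884) |
| 4 | 2.28 | 0.10 / 0.01 / 0.00 | 0.09 | 1.99 (0.916) | 1.98 (0.913) |
| 4 | 3.0 | 0.35 / 0.07 / −0.03 | 0.29 | 1.97 (0.911) | 1.94 (0.903) |

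At baseline 4 and the limiting SD of 3.33, the loss at 10% missing is 0.04.

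**Step 4, simulation.** This used three arms of 75, bounded integer scores, normal-model imputation and ANCOVA, with 400 trials and 10 imputations each. Compared with unbounded imputation, the bounded version shrank the 0.5% difference by 0.058, 0.044 and 0.016 at baselines 1, 2 and 4 with 10% missing, and by 0.119, 0.098 and 0.050 with 20%. Unbounded imputation matched the full-data difference to within about 0.015.

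**Step 5, responder cut-offs.** For an integer baseline, dropping the rounding lowers the probability that an imputed change counts as ≥5 by P(X ≥ 4.5) − P(X ≥ 5). With SD 2.28 to 3.0 this is 2-3 percentage points on placebo, 5-6 on 0.5% and 6-8 on 1.0%. Unrounded values would therefore bias a key secondary endpoint (SAP 3.1.2) toward the null.

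**The case against.** The strongest reply is that the premise and the size are both assumed. No baseline MGYLS is reported. The response threshold of more than 2 glands belongs to Cohort 1 in the protocol and is only exploratory in SAP 3.1.3.1. The entry limit of MGS ≤12 on a 0-45 scale, with about half the patients below 6, makes a low MGYLS plausible but does not establish it. No dropout rate is given, and mapping early-termination and unscheduled results to the nearest visit (SAP 5.1) will reduce Month 3 missingness. At 10% missing the loss is 0.04-0.08 even with a low baseline, about a tenth of the 0.593 standard error, and it is conservative. All of this stands and is why the point is minor. It does not restore any benefit from the bounds.

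A reader might draw stronger conclusions that the documents do not support:
- **That MGYLS is known to sit near its floor.** It is an inference, and the effect nearly vanishes at a baseline of 4 to 5 if the residual SD is moderate.
- **That false positives increase.** With equal arm means and equal missing shares, all arms shift alike.
- **That the three treatment indicators, which sum to 1, break the imputation.** One is redundant, but treatment is fully observed in the ITT Set and no numerical consequence has been shown.
- **That the primary OSDI endpoint has two rival imputation rules.** The section specific to the primary analysis names the total; the general sentence needs only a wording change.

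**Conclusion.** The concern holds as a minor one. The prespecified floor at 0 biases the primary MGYLS difference toward zero. For 0.5% against placebo the loss is about 0.04-0.08 of 2.0 units at 10% missing and 0.08-0.16 at 20%, if the baseline mean is 1-2 and the residual SD 2.28-3.0. At 10% missing that costs about one to two points of power; at 20%, two to five. With a baseline of 4 and 10% missing the loss is about 0.01-0.03, and below 0.05 even at the limiting SD.

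The direction follows from the common variance and the lower placebo mean; shrinkage was zero or positive in every case run. The size rests on the assumed baseline, residual SD and missing share. The power figures ignore information lost to missing data. The statement on type I error assumes similar missing shares by arm.

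**What to change.** For the continuous change-from-baseline analyses of MGYLS and OSDI, remove MINIMUM=, MAXIMUM= and ROUND= for the visit variables in the PROC MI calls (SAP 5.3.1.1 and 5.3.1.2) and analyse the raw imputed values. For responder endpoints such as MGYLS change ≥5, round the imputed values to the integer scale before applying the cut-off; do not use unrounded values there.

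Two tidy-ups belong in the same edit: drop one of the three treatment indicators, and align SAP 5.3 with 5.3.1.1 so that the OSDI total is the imputed quantity for the primary endpoint.

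The cost is a few lines of pseudocode and a sentence or two of text. Some imputed values in the continuous analysis will fall outside the scale, and responder derivation needs its own rounding step.

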5.3.1.2. Multiple Imputation for Exploratory Analyses

A second multiple imputation will be performed similarly for each assessment, utilizing the data through Month 6, for exploratory efficacy analyses performed after the completion of the safety follow-up period. For each of the initial 20 imputations created through Month 3, an additional 20 imputations will be created to impute Month 4.5 and Month 6. Subsequent analyses of the 20×20=400 imputations will be performed separately for each imputation, then results combined using PROC MIANALYZE.

The following pseudocode will be used, in addition to the prior pseudocode:

```

proc mi data=yyy (rename=( _imputation_ =Imp1)) seed=1357902 nimpute=20 out=zzz
  minimum = 0 0 0 18 0 0 0  0  0  0  0  0  0
  maximum = 1 1 1 99 1 1 1  xx xx xx xx xx xx
  round =   1 1 1 1  1 1 1  1  1  1  1  1  1 ;

  by Imp1;

var Dur5yr MGSless6 male age trt0_5 trt1_0 trtpbo
    Day1 Day14 Day45 Day90 Day135 Day180;

mcmc chain=multiple displayinit;
run;

```

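### The primary imputation model enters a redundant treatment indicator, shares one covariance across arms of unequal spread, and conflicts with SAP 5.3 on whether OSDI items or totals are imputed

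*SAP*

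**What the plan says.** SAP 8.1 and 8.1.1 apply multiple imputation to the primary analyses, so the model in 5.3.1.1 feeds all four hierarchical tests (MGYLS and OSDI total score, each dose against placebo).

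That model is introduced with "The following variables will be included in the multiple imputation model, as numeric variables". The list includes "Treatment group (split into three dichotomous variables", the two randomization factors, age, sex, and "Analysis value (MGYLS or OSDI total score) for each scheduled visit". The code has "var Dur5yr MGSless6 male age trt0_5 trt1_0 trtpbo" followed by four visit values, and imputes with "mcmc chain=multiple displayinit". There is no BY treatment statement, so one model covers all three arms. SAP 5.3.1.2 uses the same seven leading variables with six visit values.

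The general section, SAP 5.3, puts it differently: "Actual item results will be imputed, and any subscale scores, total scores, changes from baseline, responder status, etc. will be derived". It adds that this derivation is done only as needed.

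**The concern.** There are three separate faults in one specification.

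- Three indicators for three arms carry a redundant column. A multivariate-normal MCMC works with the covariance matrix of all listed variables, and that matrix cannot be inverted. The SAP does not say what happens then.
- With treatment entered only as indicators, arms may differ in mean but must share slopes and residual covariance. The plan's own Table 1 shows unequal spread. Imputed values then carry too much noise in the less variable arm and too little in the more variable one, and the standard error of the treatment difference inherits the error.
- Imputing OSDI items and summing them is a different procedure from imputing the total. For a primary endpoint the SAP must name one.

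What is at stake is whether the primary result can be reproduced from the SAP alone, and the accuracy of its standard errors. It is best settled before the Month 3 freeze, after which the analysis team is unmasked (SAP 1.2).

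**Working it through.** **1. The plan's own figure.** Inputs are the SAP Table 1 means and SDs. The comparison that sets the sample size is OSDI, 1.0% against placebo: difference 5.33 − 0.81 = 4.52, SDs 8.39 and 6.31. For 95% power at two-sided 0.05:

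n = (1.960 + 1.645)² × (8.39² + 6.31²) / 4.52² = 13.00 × 110.21 / 20.43 = 70.1, so 71 by normal approximation and 72 by t-test.

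The stated 72 per arm reproduces, so the plan itself relies on these arm-specific SDs.

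**2. Rank.** The Month 3 list has 4 covariates + 3 indicators + 4 visits = 11 variables. Because trt0_5 + trt1_0 + trtpbo = 1 for every patient, that sum has variance zero. With 75 of 225 patients per arm, each indicator has variance (1/3)(2/3)(225/224) = 0.2232 and each pair has covariance −(1/9)(225/224) = −0.1116. Each row sums to 0.2232 − 2 × 0.1116 = 0. Numerically the rank is 10 of 11, with smallest eigenvalue about 5e-15. Dropping one indicator gives rank 10 of 10, with smallest eigenvalue 0.49. The Month 6 list has 4 + 3 + 6 = 13 variables and the same redundancy, so its rank is at most 12.

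**3. Does the redundancy change the imputations?** With an intercept, two indicators span the same space as three. Using a generalised inverse, the conditional means under the two codings differ by at most 5e-14, and the residual variance is 8.622 under both.

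**4. Spread (Table 1, change to Month 3).**
- MGYLS: 4.11² / 2.28² = 16.89 / 5.20, a variance ratio of 3.25.
- OSDI: 9.06² / 6.31² = 82.08 / 39.82, a variance ratio of 2.06.

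The MGYLS root-mean-square SD is √[(5.20 + 11.22 + 16.89)/3] = 3.33. A shared value is therefore too large for placebo (2.28) and too small for 1.0% (4.11).

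**5. Effect on the standard error.** The documents give no missingness rate and no between-visit correlation. The table assumes correlation 0.5, uses the Table 1 MGYLS SDs, and rests on 1,500 simulated trials. It compares the mean SE with the true SD of the estimate.

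| Missing at Month 3 (placebo / 0.5% / 1.0%) | Comparison | Shared covariance | By arm |
|---|---|---|---|
| 15 / 15 / 15% | 0.5% vs placebo | about 2% too wide | within about 2% |
| 5 / 15 / 25% | 1.0% vs placebo | about 5% too narrow | within about 2% |
| 25 / 15 / 5% | 0.5% vs placebo | about 7% too wide | within about 2% |

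The simulation error on each ratio is about 1/√(2 × 1,500) = 1.8%. Further runs on the same assumptions agree within that error:
- 3,000 runs with unpooled variances. At 5/15/25%: 0.569 / 0.600 = 0.948, about 5% too narrow. At 25/15/5%: 0.546 / 0.497 = 1.099, about 10% too wide; by arm 0.511 / 0.497 = 1.028.
- Equal missingness of 5, 10 and 20%. Imputing by arm moves the SE for 0.5% vs placebo from 0.553/0.565/0.592 to 0.553/0.560/0.583, at most (0.592 − 0.583)/0.592 = 1.5%.
- Null rejection for 1.0% vs placebo at 5/15/25%. It is 7.0% shared against 5.0% by arm (simulation error about 0.6 points), and 6.9% against 5.8% in the 3,000-run set.

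**6. Items or totals.** SAP 5.3 takes items as the imputed quantity and derives totals. The variable list and code in 5.3.1.1 take the MGYLS or OSDI total score at each visit. Both cannot describe the primary OSDI imputation.

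**The case against.** The strongest reply is that little of this can be shown to move the primary result.

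- The indicators are fully observed, and the listing is labelled pseudocode. A reader might infer that the draw is undefined or the result biased. The documents do not say how the software treats a singular matrix, and step 3 shows that a generalised inverse gives the imputations that two indicators would give. This stands: it is a specification fault with no shown bias.
- A reader might also infer that a failure would first appear after unmasking. That does not follow. The indicators sum to 1 under any allocation, so a dry run with dummy codes would expose it earlier.
- The ANCOVA in SAP 8.1.1 itself assumes one residual variance. In a three-arm fit with complete data, the SE for 0.5% vs placebo is 3.33 × √(2/75) = 0.544 against a true √[(5.20 + 11.22)/75] = 0.468. That error is larger than any caused by the imputation. This also stands. However, 8.1.1 also provides for a model of each dose against placebo, and a weakness in the analysis model is no reason to repeat it in the imputation.
- The Table 1 SDs are LOCF changes from earlier studies, whereas the model imputes visit values. The spread argument is also weaker for OSDI. Both limits are fair.
- A 400-run simulation at 15% missing and correlation 0.7 gives 0.5196 / 0.4916, about 6% too wide. Its simulation error is 1/√800 = 3.5%, so it should not be read as the expected size.
- Section 5.3.1.1 is the more specific text and could be taken to govern. That resolves the item conflict only by inference. A reader might further infer that N/A answers would be filled in. No passage says so, and SAP 5.2.6 states that "questions answered with N/A are considered unanswered and excluded from the calculation".

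**Conclusion.** The point holds as a specification correction to the primary analysis that should be made.

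- **Certain from the text:** the matrix is singular in both 5.3.1.1 and 5.3.1.2, one covariance is imposed on all arms, and 5.3 conflicts with 5.3.1.1 on the imputed quantity for OSDI.
- **Conditional:** the SE error from the shared covariance. It is about 2% at equal missingness, and about 5% too narrow to 7% too wide when missingness differs by arm. These sizes rest on assumed missingness and correlation 0.5, and on earlier-study SDs carrying over. Because the sign depends on which arm loses more data, the shared model cannot be called conservative.
- **Not supported:** that the imputation is biased by the redundancy, that it must fail, or that fully observed OSDI totals would be altered.

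**What to change.** Before the Month 3 freeze:

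1. In 5.3.1.1 and 5.3.1.2, run PROC MI separately by randomized arm with Dur5yr, MGSless6, male, age and the visit values, and remove the three indicators. This removes the singularity and gives each arm its own covariance. At minimum, drop trtpbo in both sections, which cures only the singularity.
2. In 5.3, replace the general sentence for the primary endpoints with a statement that MGYLS and the OSDI total are the imputed quantities. Say which rule applies to the OSDI subscales.
3. Run the final code once on dummy treatment codes.

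The cost is SAP wording and code. The downside is fewer patients per imputation model: 8 variables on about 75 patients at Month 3, and 10 variables at Month 6. The ANCOVA's own common-variance assumption remains and is not cured by this change.
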